## 5 Study Setting

This study is set within the boundaries of Yorkshire Ambulance Service. YAS serves a population of over five million people and covers 6000 miles of varied terrain from the isolated Yorkshire Dales and North York Moors to urban areas including Bradford, Hull, Leeds, Sheffield, Wakefield and York.

## 6 Participant Eligibility Criteria

### 6.1 Inclusion criteria

Inclusion 1  
(for Cohort 1 ED  
information)

- Age 18 years old or older.
- Transported to ED by Yorkshire Ambulance Service between July 1st 2019 and December 31st 2019.
- Have an ED Care record of the event.

Inclusion 2  
(for Cohort 1  
Ambulance  
information)

- Age 18 years or older.
- Assessed by a qualified ambulance clinician ((either paramedic (of any level) or technician grade II)).
- Had an electronic patient care record completed.
- Transported to an ED between July 1st 2019 and December 31st 2019.
- Were handed over and booked in as a patient to the ED

Inclusion 3  
(for Cohort2)

- Age 18 years or older.
- Assessed by a qualified ambulance clinician (either paramedic or technician grade II).
- Had an electronic patient care record completed.
- Discharged on scene and not transported between July 1st 2019 and December 31st 2019.

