# 2 Rationale

This research is supporting paramedics to make more appropriate and effective decisions for patients who may not require the level of care provided by a hospital. It is important as it is aiming to navigate care decisions that will safely provide patients with the right care, first time. If a paramedic can see the likelihood that their patient may have an avoidable attendance, it opens up an opportunity to explore community options. It also empowers the patient to be an active partner in developing a self-care plan. The whole urgent and emergency care system would benefit from this research. If paramedics can make safe non-transport decisions it frees their capacity to assess a patient still waiting for help. With less patients being transported to the ED with low acuity problems, it will minimise delays in caring for those who do need specialist ED interventions. For community care it will identify patients that require out of hospital services so that they can get the right level of care promptly. This project does recognise when a paramedic assesses a patient, there are six possible outcomes relating to a transport decision. Firmer evidence surrounding outcome measures for the other five dispositions is needed before tools that can accurately signpost patients to any service can be developed.

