### 6.2 Exclusion criteria

Exclusion 1  
(for ED cohort)

- Patient cases where they were less than 18 years old at time of episode.
- Patient cases where there were five or more attendances within the data collection period.

Exclusion 2  
(for Ambulance  
Service cohort 1)

- Patient cases where they were less than 18 years old at time of episode.
- Patient cases where they had five or more patient contacts within the data collection period.

Exclusion 3  
(for Ambulance  
Service cohort 2)

- Patient cases where they were less than 18 years old at time of episode.
- Patient cases where they had five or more patient contacts within the data collection period.
- Patient cases that were transported by the ambulance crew on scene.

[figure not shown]

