### 7.3.2 Predictors

There will be no a priori candidate variables selected. Instead, all clinical variables collected during the paramedic patient assessment and/or treatment will be included in the initial development. Lower Super Output Area (LSOA) will be recoded into an Index of Multiple Deprivation (IMD) score which will be used as a predictor. It is anticipated there will be twenty three variables across three domains as described by table 1. Penalisation will be used in logistic regression to eliminate variables which have little or no effect on the outcome. Such methods include Ridged, LASSO and Elastic Net.

Table 1: Example of possible candidate predictors

Physical factors	Social factors	Interventional factors
Age	Location	Airway
cABC (initial assessment)	Dementia	Drug administration
Working impression	Communication	Cannulation
Allergies	DOLS	Resuscitation
Medication	Mental capacity	Extrication
Primary NEWS	Moving and handling aids	Clinical procedures
Subsequent NEWS	Mobility	Patients advice
FAST	IMD	

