## 7.4 Secondary outcome analysis

### 7.4.1 Sample size for cohort 2

This will be the maximum number of non-conveyed patients that can be attained in the same data collection period as cohort 1. A YAS report has established there were 93,271 non-conveyed patients between July and December 2018. With a 5% demand increase for 1 year forecasting, and assuming there will be no change in the percentage of non-conveyed, the sample size estimation would be 97,935.

### 7.4.2 Data preparation and missing data for cohort 2

This is the unlinked ambulance service data and only includes patients that were not conveyed to hospital. Its purpose is to sense check the derived models performance in a sample of low-mid acuity patients. All variables will be explored with a frequency analyses undertaken to identify missing data. The same preparation and methods for dealing with missing data will take place in the ambulance clinical variables as cohort 1 (see protocol section 10.3.1). No outcome will be generated as it is unlinked.

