### 7.4.4 Model selection

Once all adjusted models have been created and tested on cohort 2, there will be a comparative analysis of model performance using the same methods described above. The CI will then present the models to a small expert panel for independent confirmation. This panel will be a combination of clinicians and statisticians.

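### The low-to-mid acuity check is assigned to a cohort without an outcome, so every accuracy figure will come from the all-acuity conveyed cohort

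*Protocol*

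**What the plan says.** **Who supplies outcomes.** Protocol section 6.1 builds cohort 1 from adults assessed by a qualified ambulance clinician, with an electronic care record, who were transported and "Were handed over and booked in as a patient to the ED". On the ED side they must "Have an ED Care record of the event". Apart from age, section 6.2 removes only frequent users: on the ambulance side, "Patient cases where they had five or more patient contacts within the data collection period". Neither section sets a criterion on acuity.

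**What the models see.** Under section 7.3.2, "all clinical variables collected during the paramedic patient assessment and/or treatment will be included in the initial development". Table 1, headed as examples, lists cABC, Primary and Subsequent NEWS, FAST, Airway and "Resuscitation".

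**Where performance is measured.** Section 7.3.3 plans sensitivity, specificity, PPV, NPV, the C-statistic and a calibration plot for each model. Section 7.3.1 prefers to use the whole dataset, with resampling to correct optimism. Section 7.4.4 has the models tested on cohort 2, after which "there will be a comparative analysis of model performance using the same methods described above". Section 3.2.2 names misclassification rate among the secondary outcome measures.

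**The check in less acute patients.** Section 7.4.2 says of cohort 2: "Its purpose is to sense check the derived models performance in a sample of low-mid acuity patients". It also states that cohort 2 is unlinked and that no outcome will be generated.

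**Subgroups.** Section 7.4.3 plans performance in cohort 1 split by individual variables. It names no variable and is not tied to section 7.4.4.

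**Purpose.** Section 2 sets out to help paramedics decide about people for whom hospital-level care may be unnecessary.

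**The concern.** Two parts of the plan do not fit together. The plan sees that performance in less acute patients matters and sets up a check for it. The sample given that job cannot yield a performance measure, because each one compares a prediction with an observed outcome. For the same reason, the methods of section 7.3.3 cannot be carried over to cohort 2 when models are compared.

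What remains is cohort 1 at all levels of acuity. Some of those patients, such as those being resuscitated, are probably easy to classify as non-avoidable. Whole-cohort discrimination then mixes two tasks: telling very ill patients from the rest, and telling avoidable from non-avoidable attendances where the paramedic has a choice. Only the second supports the decision described in section 2. A reader of the final report would have no figure for it.

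**Working it through.** **Plan's own figure.** The protocol states no expected accuracy and no acuity mix for conveyed patients, so there is no figure to reproduce. The calculation shows direction and an upper bound under stated assumptions.

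**Inputs**
- Event rate: 9% (section 7.2); 16.9% is the upper figure quoted in section 1.
- C in patients with an open decision: 0.70 (assumed).
- f, the share of non-events that is high acuity: 10%, 20% and 30% (assumed).
- High-acuity patients have no events and are all ranked below every event (assumed). This makes each result an upper bound for its f.
- Threshold giving 80% sensitivity, with equal-variance normal scores (assumed).

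**C-statistic.** An event is paired with a high-acuity non-event with probability f and is then always ranked correctly. Otherwise the pair is ranked correctly with probability C. Hence C_all = f + (1 − f) × C.
- f = 10%: 0.10 + 0.90 × 0.70 = 0.73
- f = 20%: 0.20 + 0.80 × 0.70 = 0.76
- f = 30%: 0.30 + 0.70 × 0.70 = 0.79

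The event rate does not enter.

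**Threshold measures, per 1,000 patients at 9% and f = 30%.**
- Specificity in the decision group is Φ(√2 × Φ⁻¹(0.70) − Φ⁻¹(0.80)) = Φ(0.742 − 0.842) = 0.46.
- There are 90 events: 72 true positives and 18 false negatives.
- There are 910 non-events: 273 high acuity and 637 with an open decision.
- Of the 637, 0.46 × 637 = 293 are true negatives and 344 are false positives.
- The 273 are all true negatives.

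| Measure | Decision group (n = 727) | Whole cohort (n = 1,000) |
|---|---|---|
| C-statistic | 0.70 | 0.79 |
| Specificity | 293/637 = 0.46 | 566/910 = 0.62 |
| NPV | 293/311 = 0.94 | 566/584 = 0.97 |
| Misclassification | 362/727 = 0.50 | 362/1,000 = 0.36 |
| Sensitivity | 72/90 = 0.80 | 72/90 = 0.80 |
| PPV | 72/416 = 0.17 | 72/416 = 0.17 |

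The added patients are all true negatives, so sensitivity and PPV do not move. At an event rate of 16.9% and the same f, misclassification is 0.46 in the decision group and 0.35 overall.

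**Ranking of models.** With the same f for every model, C_all rises strictly with C. If model A beats model B in the decision group, it also beats it overall. The order can differ only if the models rank the high-acuity patients differently.

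**Scale.** Section 2 cites areas under the curve of 0.807 and 0.743 for two admission tools, a gap of 0.064. The shift at f = 20% is at most 0.06. Those tools predict a different outcome, so this gives only a sense of size.

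**The case against.** The other side has a good deal right.

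- **Population.** The primary question concerns adults without an acuity limit. The low-to-mid acuity phrase describes cohort 2, and the toolkit in section 11.1.1 has no acuity gate. A reader might infer that cohort 1 is the wrong population, or that whole-cohort figures should lose their place as the headline. The documents do not support that: all-acuity performance answers the question as posed.
- **Inflation as a fact.** A reader might conclude that reported accuracy will be substantially inflated. The size rests on assumed values and a best-case ranking. Section 1 says most calls were urgent rather than emergencies, which points towards a smaller f, and at 10% the shift in C is at most 0.03. The outcome is defined in a cited source, so whether high-acuity patients are never events cannot be verified here.
- **All accuracy measures.** Sensitivity and PPV do not change at a fixed threshold. PPV is the share of patients flagged as avoidable who truly are, and it is already planned.
- **Wrong model chosen.** A reader might infer this too. The formula shows that it does not follow when high-acuity patients are equally easy for every model.
- **Subgroups.** Section 7.4.3 could show the contrast if split on NEWS or a similar field, and such detail is often left to an analysis plan.

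The last point does not dispose of the concern. The protocol itself gives the less acute check to a cohort without an outcome, names no acuity split, and leaves subgroup results out of model selection.

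**Conclusion.** The point holds in a limited form. As written, the low-to-mid acuity check can produce no accuracy figure, and every such figure will come from linked, conveyed adults of all acuities with fewer than five contacts. This follows from the text and needs no assumption.

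The effect on reported performance is conditional. If high-acuity patients are easy non-events, whole-cohort C, specificity, NPV and misclassification will look more favourable than in patients with an open decision. With a true C of 0.70 there and 20% to 30% of non-events perfectly ranked, whole-cohort C is at most about 0.76 to 0.79. The documents fix neither value. They do not show that the eventual model choice would be wrong.

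**What to change.** - Keep cohort 1 as it is for derivation, and keep the whole-cohort results.
- In sections 7.4.3 and 7.4.4, define a lower-acuity analysis subset of cohort 1 before outcomes are examined. Use recorded ePCR fields available before the transport decision, for example Primary NEWS, cABC and FAST. Table 1 gives no timing, so confirm availability against the data specification. The expert panel in section 7.4.4 sees finished models, so the definition must be settled earlier.
- Report optimism-corrected discrimination, calibration and misclassification for every model in that subset beside the whole-cohort figures. State that both will be considered in model selection.
- In section 7.4.2, limit cohort 2 to describing the distribution of predicted risk, and reword sections 7.4.3 and 7.4.4 to match.

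This defines an analysis set and is not a clinical rule. The subset still consists of conveyed patients, so its results do not measure performance in non-conveyed patients.

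**Cost.** Protocol wording and one more run of the same metrics. The C-statistic in the subset will probably be less favourable. Precision should be little affected: the plan targets 520 × 50 = 26,000 events, and if high-acuity patients have few events, most of these stay in the subset.

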### 6.2 Exclusion criteria

Exclusion 1  
(for ED cohort)

- Patient cases where they were less than 18 years old at time of episode.
- Patient cases where there were five or more attendances within the data collection period.

Exclusion 2  
(for Ambulance  
Service cohort 1)

- Patient cases where they were less than 18 years old at time of episode.
- Patient cases where they had five or more patient contacts within the data collection period.

Exclusion 3  
(for Ambulance  
Service cohort 2)

- Patient cases where they were less than 18 years old at time of episode.
- Patient cases where they had five or more patient contacts within the data collection period.
- Patient cases that were transported by the ambulance crew on scene.

[figure not shown]
## 7 Statistics and Data Analysis

### 7.1 Data linkage plan

All patients (using the cohort 1 eligibility criteria) will be retrieved from the Yorkshire Ambulance Service data warehouse by the Business Intelligence (BI) team within the organisation. This data will not be seen by the **CI or student investigator**. Once retrieved, the data will be split into two different extracts. The first is the clinical information extract. This will be anonymised completely and delivered securely to the School of Health and Related research (SchARR) at the University of Sheffield. The second is the identifiable information extract. This will be securely sent to NHSD. They will link this data in a secure environment with the associated ED record for each patient. The methodology used is transparent and well documented. Once maximum data linkage has been achieved, the dataset will be completely anonymised and divided into 'linked' and 'unlinked' cases. This is because it is anticipated that not all cases will be able to be linked. These two datasets will then be securely delivered to the SchARR and stored appropriately in accordance with the University of Sheffield (UOS) Information Governance policies. All identifiable information will remain in NHSD and will be deleted as soon as the data is linked. The linked data will then be merged with the clinical extract. The unlinked data will be used for a bias assessment at UOS before being completely deleted. The data flow diagram for this project can be found in section ix above.

### 7.2 Sample size calculation

Numerous studies have suggested that each candidate predictor requires at least 10 Events Per Variable (EPV). All candidate predictors (twenty three) have been transposed from the YAS electronic Patient Care Record (ePCR) and can be found in table 1. These output a liberal estimation of 520 parameters, and therefore 5200 events. A study examining avoidable conveyances reported a lower limit of 9% avoidable conveyances in the same population as this study. When this is applied to the minimum number of events, it would yield a sample size of 57,778. However, one study has shown that up to 50 events per variable are needed for variable selection. This would alter the sample size to 288,889. Data linkage on the same data had a success of 80% using deterministic matching on hierarchical variables. There was also 7.7% of data which was incomplete to create the outcome variable (avoidable attendance). This would alter the potential sample size for the first cohort to 368,911. In 2018, YAS assessed 919,635 patients on scene and conveyed 735,053 (74.9%). This would mean a data collection period of 6 months in order to fulfil the sample size of 368,911.

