## 8 Data Management

### 8.1 Data collection tools and source document identification

Yorkshire Ambulance Service has an ePCR system in place across the whole region. This is a compulsory system for paramedics to create and complete individual care records for each patient which begins at arrival on scene, and is completed once the patient is handed over. This document forms the source document for each patient that will be eligible in this project. The sample size in section 10.2 is in effect calculating the number of source documentation required for model derivation and validation.

Within each source document is the variables required to derive and validate the model. An example of the variables within can be seen in table 1 (above). The variables are mainly categorical and presented as drop down lists. The other type of variable captured is continuous such as age. The clinician is expected to fully complete each record however not all fields are compulsory capture.

This is a retrospective study and as such, there will be no attempt to maximise completeness of data. The sample size has been inflated to account for expected source document attrition at the point of data retrieval. The methodology has accounted for the handling of missing data.

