##### **10.5.3 Minimum necessary for the purpose**

There will be the minimum amount of data collected which will satisfy the required sample size for the study. Only variables that will have potential to act as a candidate predictor, or are necessary for data linkage will be requested.

There will be the linkage of data from YAS, and data held by NHSD. Only data items of name, address including postcode, date of birth, age, gender, NHS number and incident/episode number are required for data linkage. A more limited number of fields are not possible to specify or collect as the nature of YAS data is such that for different cases different personal identifiers will be missing i.e. for some YAS cases, no home address will be specified as the incident may have happened away from the individuals' home. In this case age, gender and name/ NHS number will be required to enable linkage.

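### Section 7.2 adds the two loss rates instead of dividing by retention, so 368,911 records give about 46 to 47 events per parameter, not the 50 targeted

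*Protocol*

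**What the plan says.** Protocol section 7.2 builds the cohort 1 sample size in steps.

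- The candidate predictors are converted to parameters: "These output a liberal estimation of 520 parameters, and therefore 5200 events".
- For the event rate, an earlier study "reported a lower limit of 9% avoidable conveyances in the same population as this study". With 10 events per parameter, "it would yield a sample size of 57,778".
- The target is then raised, because "up to 50 events per variable are needed for variable selection". This takes the need to 288,889.
- Two losses follow: linkage succeeded for 80% of records, and 7.7% of data could not form the outcome. The result: "This would alter the potential sample size for the first cohort to 368,911".
- From 735,053 conveyances in 2018, the section concludes that six months of data fulfils that number.

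Section 8.1 gives the purpose of the last inflation: "The sample size has been inflated to account for expected source document attrition at the point of data retrieval". The Study Summary gives a planned sample size of 466,846, which is 368,911 plus the 97,935 estimated for cohort 2 in section 7.4.1.

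**The concern.** An inflated sample size should leave the required number after the expected losses. Here 288,889 is the required number, and 368,911 should shrink back to it once linkage failures and incomplete outcomes are removed. It does not. The pattern suggests that 20% and 7.7% were added together and applied to the number needed, when they are losses from the larger number retrieved. That always gives too small a figure.

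What is at stake is whether three statements are true as written: that 368,911 supports 50 events per parameter, that the planned total is 466,846 on that basis, and that six months is long enough.

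**Working it through.** **Inputs**, all from section 7.2 unless noted: 520 parameters; 50 events per parameter; event rate 9%; linkage 80%; incomplete outcome 7.7%; 735,053 conveyances in 2018; cohort 2 estimate 97,935 (section 7.4.1).

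**1. Reproduce the plan's figures.**
- 520 x 10 / 0.09 = 57,778 (matches).
- 520 x 50 / 0.09 = 288,889 (matches).
- 288,889 x (1 + 0.20 + 0.077) = 288,889 x 1.277 = 368,911.25 (matches to the unit).
- 368,911 + 97,935 = 466,846 (matches the Study Summary).

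The additive formula is inferred, since the protocol does not print it. Other candidates do not give 368,911:

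| Formula | Result |
|---|---|
| 288,889 / 0.80 (linkage only) | 361,111 |
| 288,889 x 1.20 x 1.077 | 373,360 |
| 288,889 x 1.20 / 0.923 | 375,587 |
| 288,889 / 0.80 x 1.077 | 388,917 |

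**2. Apply the stated losses to 368,911.** The protocol does not say what the 7.7% is a share of, so both readings are shown.

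| | 7.7% of linked records | 7.7% of all records |
|---|---|---|
| Retention | 0.80 x 0.923 = 0.7384 | 1 - 0.277 = 0.723 |
| Usable records | 272,404 | 266,723 |
| Events at 9% | 24,516 | 24,005 |
| Events per parameter (events / 520) | 47.1 | 46.2 |

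The target was 288,889 usable records and 520 x 50 = 26,000 events.

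**3. Records needed to meet 50.**
- 288,889 / 0.7384 = 391,237, rounded up: 22,326 more than stated (6.1%). Total with cohort 2: 391,237 + 97,935 = 489,172.
- 288,889 / 0.723 = 399,570: 30,659 more than stated (8.3%). Total with cohort 2: 399,570 + 97,935 = 497,505.

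**4. Check the six-month statement.**
- 735,053 / 2 = 367,527, already slightly below 368,911.
- That volume yields 367,527 x 0.7384 x 0.09 / 520 = 47.0 events per parameter, or 46.0 with 0.723.
- At 735,053 / 12 = 61,254 per month, 391,237 records take 391,237 / 61,254 = 6.4 months.
- If the 5% growth that section 7.4.1 uses for cohort 2 is assumed for cohort 1 too, six months gives 385,903 records and 49.3 events per parameter (48.3 with 0.723), still short of 50.

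**The case against.** The strongest reply is that the shortfall is too small to matter.

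- **The inputs are conservative.** The protocol calls 520 parameters a liberal estimate, 9% a lower limit and 50 an upper figure; its stated minimum is 10. With 272,404 usable records, 26,000 events are reached at a prevalence of 26,000 / 272,404 = 9.54%. At the 16.9% quoted in the Background, there would be 272,404 x 0.169 / 520 = 88.5 events per parameter. At 9%, cutting 520 parameters to 490 would also close the gap (24,516 / 50 = 490). Section 7.3.2 plans penalised regression as well. This stands as a limit on severity. It does not make 368,911 correct, and the protocol nowhere says that the slack is meant to absorb an inflation error.
- **Incomplete outcomes might be imputed.** Section 7.3.1 allows multiple imputation. If it covered the outcome, linkage loss alone would need about 361,111 records, fewer than stated. But section 7.2 itself counts the 7.7% as a loss, and 361,111 is not the printed figure.
- **The extract is fixed by dates.** Section 6.1 sets July to December 2019, and section 7.1 retrieves every eligible patient. This stands.

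The last reply also answers a stronger reading. From section 10.5.3 ("There will be the minimum amount of data collected which will satisfy the required sample size for the study") a reader might infer that 368,911 defines or caps the data request, so that the error changes what is collected. The documents do not support that: the number served to justify the window, and the window determines the records. Nor does an understated requirement lead to excess collection of identifiable data.

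**Conclusion.** The figure is wrong as written. At the protocol's own loss rates, 368,911 retrieved records support about 47.1 events per parameter, or 46.2 on the other reading of the 7.7%, against the 50 from which the number is built. The requirement for 50 is understated by 6% to 8%, the total of 466,846 inherits the error, and the statement that six months fulfils the requirement does not hold at the stated 2018 volume.

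This rests on the inferred additive formula, the 9% prevalence, and the 2018 conveyance count taken at face value. That count needs checking: 735,053 / 919,635 is 79.9%, not the printed 74.9%. If the percentage is the correct one, six months gives 919,635 x 0.749 / 2 = 344,403 conveyances and about 43 to 44 events per parameter.

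The correction is modest. A reader might infer that the model is underpowered or that variable selection is compromised. The protocol's figures do not support this, because 46 to 47 remains more than four times its stated minimum of 10 and is computed from deliberately cautious inputs.

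**What to change.** In section 7.2:

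- Print the formula: records to retrieve = n / (linkage x outcome completeness).
- Say whether the 7.7% is a share of linked records or of all records. If it is of all records, the divisor is 1 - 0.20 - 0.077.
- Keep the July to December 2019 window. In place of the claim that it meets 50, state that it is expected to give about 46 to 47 events per parameter at 9% prevalence.
- Reconcile the conveyance count with its percentage, since the expected yield depends on it.

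In the Study Summary, restate the planned sample size on the same basis.

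Substituting 391,237 (or 399,570) for 368,911 alone would not work. It would contradict the next sentence, because six months supplies about 367,527 conveyances, and it would strain against the fixed dates in section 6.1.

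The cost is a few sentences in 7.2 and the summary, plus the data request if it quotes the figure. No additional records are needed.

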### *Non-conveyance*

Non-conveyance can be defined as "an ambulance deployment as appropriate, where the patient after examination and/or treatment on-scene does not require conveyance with medical personnel and equipment to the healthcare facility". Ebben et al. produced a recent systematic review on the subject; focusing on patient safety and outcomes further along in the patient journey. This systematic review appears to be the most comprehensive in comparison to other reviews undertaken in the same subject area. Sixty seven studies were included in the review with the majority being quantitative observational studies. The rate of non-conveyance varied between 3.7%–93.7%. This was due to the differences in prehospital models between countries.

According to NHS England, the current non-conveyance rate experienced nationally in the UK is 37.6% (locally in Yorkshire it is 30.6%). The limitation of this report is that the data collected is used as a performance measure for the ambulance service. This could introduce a bias into the data collection stage and mar the accuracy of the report. A different approach to non-conveyance would be to ascertain clinical necessity of conveyance. Patton and Thakore found that a third of their sample attended the ED 'inappropriately' although their sample size was low (n=295).

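### Section 7.2 gives 735,053 of 919,635 as 74.9% when it is 79.9%, and its claim that six months fulfils 368,911 makes no allowance for the cohort 1 eligibility criteria

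*Protocol*

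**What the plan says.** Section 7.2 builds the cohort 1 size in steps.

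- Parameters and minimum events: "These output a liberal estimation of 520 parameters, and therefore 5200 events".
- The target is then raised because "one study has shown that up to 50 events per variable are needed for variable selection".
- Prevalence: a previous study "reported a lower limit of 9% avoidable conveyances in the same population as this study".
- The resulting 288,889 is inflated to 368,911 for 80% linkage success and 7.7% incomplete outcome data.

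Accrual follows in two sentences. The first is "In 2018, YAS assessed 919,635 patients on scene and conveyed 735,053 (74.9" (the last figure is a percentage). The second is "This would mean a data collection period of 6 months in order to fulfil the sample size of 368,911". The six-month yield itself is not shown.

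Section 6.1 fixes the window as 1 July to 31 December 2019. Sections 6.1 and 6.2 limit cohort 1 to adults taken to an ED, assessed by a qualified clinician, with a completed ePCR and fewer than five contacts. One criterion reads "Were handed over and booked in as a patient to the ED".

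For cohort 2, section 7.4.1 takes a different route: "A YAS report has established there were 93,271 non-conveyed patients between July and December 2018", increased by 5% for one year of demand growth to give 97,935.

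**The concern.** The count and the percentage in the accrual sentence cannot both be right, given the stated denominator. They differ by about 46,000 conveyances a year, which is too much for rounding.

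That sentence is the only support offered for the length of the window. The size it is said to deliver is carried into the study summary, where the planned total of 466,846 is 368,911 + 97,935.

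The 2018 figures are also presented as all patients conveyed, whereas cohort 1 is a restricted subset. Section 8.1 says the size was inflated for attrition of source documents at retrieval, yet the only inflation in section 7.2 is for linkage and outcome completeness. A reader cannot tell how many eligible records, and so how many events per parameter, the fixed window is expected to provide.

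**Working it through.** **Reproducing the plan's figure.** Events: 520 × 50 = 26,000. Records: 26,000 / 0.09 = 288,889. Inflation: 288,889 × (1 + 0.20 + 0.077) = 368,911. This matches exactly, so no eligibility loss is included.

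**The percentage.** 735,053 / 919,635 = 79.9%. Conversely, 0.749 × 919,635 = 688,807, which is 46,246 fewer than the stated count.

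**Which figure fits the rest of the protocol.** Section 7.4.1 reports 93,271 non-conveyed in July to December 2018. Half-year non-conveyed implied by each reading:

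- Count: (919,635 − 735,053) / 2 = 184,582 / 2 = 92,291, close to 93,271.
- 74.9% of 919,635: (919,635 − 688,807) / 2 = 115,414, a poor fit.
- 735,053 and 74.9% both right, 919,635 wrong: the denominator would be 735,053 / 0.749 = 981,379, giving (981,379 − 735,053) / 2 = 123,163, also a poor fit.

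The count is the better supported figure. This assumes that the 7.4.1 report and the 7.2 totals cover the same kind of patient, which the protocol does not say.

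**Six-month pool before eligibility, against 368,911.** July to December is 184 of 365 days; the 5% growth is taken from section 7.4.1.

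| Variant | On the count 735,053 | Difference | On 74.9% (688,807) | Difference |
|---|---|---|---|---|
| Simple halving | 367,527 | −1,384 (−0.4%) | 344,403 | −24,508 (−6.6%) |
| × 184/365 | 370,547 | +1,636 (+0.4%) | 347,234 | −21,677 (−5.9%) |
| Halving × 1.05 | 385,903 | +16,992 (+4.6%) | 361,623 | −7,288 (−2.0%) |
| × 184/365 × 1.05 | 389,075 | +20,164 (+5.5%) | 364,596 | −4,315 (−1.2%) |

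**Margin for the eligibility criteria, on the count.**

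- Simple halving: none.
- By days, no growth: 1 − 368,911 / 370,547 = 0.4%.
- With growth: 1 − 368,911 / 385,903 = 4.4%.
- With growth and days: 1 − 368,911 / 389,075 = 5.2%.

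The protocol gives no figure for the share of conveyances lost to these criteria.

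**Events per parameter before exclusions.** Pool × 0.80 × 0.923 × 0.09 / 520 = pool × 0.0001278.

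- Count: 367,527 gives 47.0; 370,547 gives 47.4; 385,903 gives 49.3; 389,075 gives 49.7.
- 74.9%: 344,403 gives 44.0; 364,596 gives 46.6.

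In events, the count gives about 24,424 to 25,856 against the 26,000 targeted. A pool of exactly 368,911 would itself give 368,911 × 0.0001278 = 47.1, because section 7.2 adds the two loss rates and this calculation compounds them. The gap below 50 before exclusions therefore comes from that step and should not be attributed to the length of the window.

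**The case against.** A reader might infer that six months falls short of 368,911 whichever figure is right, even before eligibility. The documents do not support that. On the count, the shortfall from simple halving is 0.4%, equivalent to needing 6.02 months, which is within the rounding of a six-month statement. It disappears when July to December is counted as 184 days, or when the protocol's own growth is applied. Omitting growth from cohort 1 understates its yield, so the inconsistency with cohort 2 is no evidence of a shortfall. Only the 74.9% reading is short throughout, and it is the less credible one: it differs from the correct value by a single digit and does not fit section 7.4.1.

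A reader might also set the yield against 391,236, which is 288,889 / (0.8 × 0.923). That tests how the loss rates were combined, which is a separate question from whether the window delivers the size the protocol states.

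Nor does the background section's statement that "the current non-conveyance rate experienced nationally in the UK is 37.6% (locally in Yorkshire it is 30.6" per cent) settle the matter. It comes from a report cited as 2017, whose accuracy the protocol itself questions, and cannot be applied to 2018 counts.

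The practical effect is small. The inputs are conservative: 9% is described as a lower limit, the background cites up to 16.9%, and 520 parameters is called liberal. At the simple-halving volume, 50 events per parameter is reached at a prevalence of 26,000 / (367,527 × 0.7384) = 9.6%. Penalised regression is planned. The ED-record criterion overlaps with the 80% linkage rate, so it should not be deducted again.

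These arguments limit the size of the point. They leave standing the wrong figure and the absence of any allowance for the other criteria.

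**Conclusion.** Section 7.2 contains an arithmetical conflict that must be reconciled, most likely by changing the percentage to 79.9%. Its statement that six months fulfils 368,911 is not demonstrated, because it compares the target with conveyances of all patients.

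On the better supported count, there is no margin for the cohort 1 criteria with simple halving and about 4.4% to 5.2% with growth. Whether actual exclusions exceed that cannot be determined from the protocol, so it would be wrong to conclude that the window certainly fails. If 74.9% were right, the pool would be short in every variant, by 1.2% to 6.6%.

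The consequence is modest: about 47.0 to 49.7 events per parameter before exclusions on the count, against 50 targeted and the minimum of 10 cited in section 7.2. This rests on the protocol's 80% linkage, 92.3% outcome completeness, 9% prevalence and 520 parameters. The study is not invalidated; its sample size justification is wrong as written.

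**What to change.** 1. Correct the percentage or the count in section 7.2 so that they agree with 919,635.
2. Replace the annual figure with a July-December 2018 count of conveyances meeting the cohort 1 criteria, and apply the same 5% growth as for cohort 2. Do not deduct the ED-record criterion separately where the linkage rate already covers it.
3. Restate the expected usable records, events and events per parameter for the fixed window, in place of the claim that it fulfils 368,911. Carry the new figure into the planned sample size in the study summary.

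The cost is one query by the ambulance service's Business Intelligence team and a short text amendment. No extra patients or longer window are needed. The stated events per parameter becomes slightly less favourable.
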